8.5. ACCOUNTABILITY OF RZL-012 AND VEHICLE

The RZL-012 investigational product was manufactured by PharmaCore (USA) and complies with cGMP requirements. Formulation and packing were done by Nextar (Israel) and complies with cGMP requirements.

The vehicle was manufactured and packed by Nextar (Israel) and complies with cGMP requirements.

The RZL-012 investigational product and vehicle will be supplied in kits, in quantities as needed to comply with the treatment of site subjects according to the study protocol.

Site coordinator will notify the Sponsor or its official designee, in a timely manner and no less than 14 working days in advance, of any supply requirements to prevent shortage.

Shipment, storage and inventory documentation will be updated regularly and kept in the investigation files at the site to allow inspection and trace of the supplied product.

9. ADVERSE EVENTS

9.1. ADVERSE EVENT DEFINITIONS

9.1.1. Definition of AE

An AE is defined as any untoward medical occurrence in a clinical investigation subject administered a pharmaceutical product and which does not necessarily have to have a causal relationship with this treatment. An AE can therefore be any unfavorable and unintended sign (including an abnormal laboratory finding, for example), symptom, or disease temporally associated with the use of a medicinal product, whether or not considered related to the medicinal product. This definition includes any abnormalities or anomalies that were not seen at baseline or which worsened during the course of the study, if present at baseline.

9.1.2. Definition of Serious Adverse Event

A SAE is defined as any AE occurring at any dose that results in any of the following outcomes:

- death
- a life-threatening AE, as defined below
- subject hospitalization or prolongation of existing hospitalization
- a persistent or significant disability/incapacity
- a congenital anomaly/birth defect
- important medical event, as defined below

A life-threatening AE is any AE that places the subject, in the view of the investigator, at immediate risk of death from the reaction as it occurred (i.e., it does not include a reaction that, had it occurred in a more severe form, might have caused death).

An important medical event is an AE that may not result in death, be life-threatening, or require hospitalization but may be considered a serious AE when, based upon appropriate medical judgment, may jeopardize the subject and may require medical or surgical intervention to prevent one of the outcomes listed above. It can also include AEs otherwise judged to be serious by either the investigator or the Sponsor.

9.1.3. Definition of Adverse Drug Reaction

AEs associated with the use of investigational product (i.e., probably or possibly related to treatment as defined in Section 9.3) are also termed ADRs.

9.2. ADVERSE EVENT GRADING

AE will be documented in each study visit.

AEs severity will be graded as follows:

- Mild (Grade 1): Sign or symptom, usually transient, requiring no special treatment and generally not interfering with usual activities.
- Moderate (Grade 2): Sign or symptom, which may be ameliorated by simple therapeutic measures, may interfere with usual activity.
- Severe (Grade 3): Sign or symptom that is intense or debilitating and that interferes with usual activities and/or requires hospitalization. Recovery is usually aided by therapeutic measures and the discontinuation of the study product may be required.
- Life-threatening or disabling (Grade 4): Sign or symptom that is life-threatening or disabling.
- Death (Grade 5): Death related to AE.

9.3. CAUSALITY ASSESSMENT OF ADVERSE EVENTS

All AEs will be evaluated by the investigator and assigned an estimated relationship to the RZL-012 investigational product. The terms "related" or "unrelated" refer to the association with the use of the investigational product, as defined below in Table 6.

Medical judgment should be used to determine the relationship, considering all relevant factors, including pattern of reaction, temporal relationship, confounding factors such as concomitant medication, concomitant diseases and relevant history.

Assessment of causal relationship should be recorded directly in subjects' CRF.

Definition of AEs causality is specified in the table below (Table 6).

RZL-012-SMF-P2US-001 Version: 1.2

Table 6: Definition of Causality

TERM	DEFINITION	CLARIFICATION
Unrelated	This category applies to those AEs which, after careful consideration, are clearly due to extraneous causes (disease, environment, etc.)	
		•
		•
		•
Related	This category applies to those AEs which, after careful medical consideration at the time they are evaluated, are felt with high degree of certainty to be related to the study procedures/investigational product.	An AE may be considered related if or when all of the following apply: It follows a reasonable temporal sequence from study procedures/administration of the investigational product. It could not be reasonably explained by the known characteristics of the subject's clinical state, environmental or toxic factors, or other modes of therapy administered to the subject. It disappears or decreases on cessation or reduction in dose. There are important exceptions when an adverse event does not disappear upon discontinuation of the investigational product, yet investigational product-relatedness clearly exists. It follows a known pattern of response to the study procedures/investigational product.

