6.2.3. Study Treatment

6.2.3.1. Treatment with RZL-012 Investigational Drug to Submental Fat

RZL-012 or placebo is an investigational product supplied as a single treatment in multiple sites of injections (48 injections).

The injection dosing regimen and technique is crucial for the therapy safety.

The following procedures prior to injection into the submental fat will be applied:

- 1. The lower face and anterior neck will be cleaned with an appropriate topical antiseptic.
- 2. Ice/cold pack or topical local anesthesia (i.e., lidocaine cream) may be used prior to RZL-012 administration to enhance subject's comfort.
- 3. The treatment area will be bounded superiorly by a line 1 cm inferior to the mandibular margin, laterally by the sternocleidomastoid muscles, and inferiorly by the hyoid bone.
- 4. Injection grid pattern will be applied by pressing the grid firmly onto the clean dry skin, where the printed grid pattern facing the skin. The grid paper backing will be thoroughly wetted with a cotton pad soaked with sterile water. Following 15 seconds waiting, the grid cover will be peeled off.
- 5. The number of injections and injection volume in each cohort will be determined following physician's evaluation.
- 6. Syringes will be filled with 0.5 mL (Cohort 1) or 1 mL (Cohort 2) RZL-012 or vehicle and the number of syringes will be compatible with the total volume of injection. Up to 5 syringes for a total volume of 2.4 mL (each syringe having a volume of 0.5 mL) or up to 5 syringes (each syringe having a volume of 1 mL) for a total volume of 4.8 mL. See table below for details on injection of both cohorts:

Cohort	Syringe volume	Injection volume of RZL- 012/placebo	No. of injections	Total injected volume of RZL-012 or placebo	Amount of injected RZL-012
1	0.5 ml	0.05 ml	Up to 48	Up to 2.4 mL	Up to 120 mg
2	1 ml	0.1 ml	Up to 48	Up to 4.8 mL	Up to 240 mg

- 7. All injections will be administered diagonally in 90°, using a 0.5 mL syringe (Cohort 1) or 1 mL (Cohort 2) Luer-lock syringe and a 29/30 G x 1/2" needle, respectively.
- 8. The hole of the needle should be pointing into the fat layer and the injection direction should be towards the earth. An attempt to pull the plunger should be made before injecting to ensure that no blood is coming out. If so, the plunger should be pushed down to inject the medicine. The formulation is viscous; therefore, a resistance is expected while injecting.

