9.5. ADVERSE EVENT REPORTING AND MONITORING REQUIREMENTS

9.5.1. General

All AEs, serious and non-serious, will be fully documented in both source documents and CRFs as described in Section 6.1.14, and each AE will be assessed in light of its clinical significance. For each AE, the investigator will provide the onset, end, intensity, treatment required, outcome, seriousness and action taken with the investigational drug. The investigator will determine the relationship to the investigational drug, i.e., causality assessment, for each AE.

Any AE occurring prior to initiation of first dose, after initiation of the first dose and or during any point throughout the study should be recorded on the AE page of the CRF. All AEs occurring until subject is terminated from the study (84 days after the injection of RZL-012), should be captured in the CRF. AEs should be recorded in the CRF using the medical

terminology found in the source documentation. Whenever possible, diagnoses should be given when signs and symptoms are due to a common etiology.

Occurrence of any serious or severe ADR must warrant clinical evaluation by the treating investigator and reported to the Sponsor/medical monitor within 24 hours.

ADRs will be followed-up until resolution, or for a maximal duration of 6 months after RZL-012 injection, whichever occurs first.

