10.2.3. Safety and Tolerability Endpoints

Safety endpoints include:

- Incidence of AEs and SAEs, by severity and relation to study treatment of RZL-012 vs. placebo treated subjects. AEs will be coded using MedDRA version 22 (or higher).
- Specific AEs will be closely monitored: bruising, pain, induration and swelling/ Edema and Erythema (Draize Score).
- Vital signs

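### The causality target is worded inconsistently, is judged by an unmasked investigator and decides who is followed past Day 84, so related-event tables, and durations of reactions still open at Day 84, can be biased between arms

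*Combined protocol and SAP*

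**What the plan says.** The causality target differs from place to place in the combined protocol and SAP.

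- The lead sentence of Section 9.3: "All AEs will be evaluated by the investigator and assigned an estimated relationship to the RZL-012 investigational product". Section 9.5.1 repeats the idea, with the investigational drug as the target.
- Table 6, also in Section 9.3, is wider. An event is related when it is "felt with high degree of certainty to be related to the study procedures/investigational product". The first criterion is: "It follows a reasonable temporal sequence from study procedures/administration of the investigational product".
- Section 9.1.3 defines ADRs as "AEs associated with the use of investigational product", with a parenthesis that points to relatedness to treatment under Section 9.3. It does not mention procedures.
- Section 6.2.3.1 treats placebo as an investigational product: "RZL-012 or placebo is an investigational product supplied as a single treatment in multiple sites of injections (48 injections"). Section 8.5 names the investigational product and the vehicle separately.

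Follow-up depends on that judgement. For all events, Section 9.5.1 says: "All AEs occurring until subject is terminated from the study (84 days after the injection of RZL-012), should be captured in the CRF". For ADRs alone it adds: "ADRs will be followed-up until resolution, or for a maximal duration of 6 months after RZL-012 injection, whichever occurs first".

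Section 6.2.2 leaves the investigator and clinical staff unmasked.

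On reporting, Sections 4.1 and 10.2.1 make frequency, severity and duration of the local reactions the primary endpoint, RZL-012 against placebo. Section 4.1 refers to events related to the injection procedure, and Section 10.5.1 tabulates injection-related events by treatment. Section 10.2.3 lists: "Incidence of AEs and SAEs, by severity and relation to study treatment of RZL-012 vs. placebo treated subjects".

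**The concern.** The endpoint is worded around the injection procedure, which both arms undergo. The lead sentence of Section 9.3 asks a different question: was it RZL-012? An investigator who knows that a subject received vehicle, and who works from that sentence, has reason to answer no for bruising or induration. Section 7.2 adds to this by describing the target skin events as associated with the RZL-012 product. An investigator who works from Table 6 can answer yes for the same event. Two sites could therefore code identical vehicle reactions differently.

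Two outputs are exposed:

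- **Related-event tables by arm.** Under-attribution in the vehicle arm would widen the apparent difference.
- **Duration.** The same judgement decides whether observation continues after Day 84. The plan gives no common window and no censoring rule for duration; Section 10.6 says only that missing data are not imputed. A reaction open at Day 84 could then have a longer recorded duration in one arm because it was watched for longer.

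**Working it through.** The plan states no rate, power or duration figure for this point, so there is nothing to reproduce. The attribution rates and duration distributions below are assumptions that show the range.

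**1. One vehicle reaction under each text.** Take induration in a vehicle subject.
- Lead sentence of 9.3, read literally: not related to RZL-012.
- Table 6: can be related, because it follows a study procedure.
- 9.1.3: an ADR only if vehicle counts as investigational product. Section 6.2.3.1 suggests that it does; the separate listing in 8.5 suggests that it does not.

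So the texts allow either coding, and either length of follow-up.

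**2. Related-event tables.** Let p be the true reaction rate, equal in both arms. Let every active reaction be attributed, and a fraction q of vehicle reactions.

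Apparent difference = p − p·q = p(1 − q)

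With p = 0.50:
- q = 0 gives 0.50
- q = 0.5 gives 0.25
- q = 1 gives 0

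On all-causality counts the difference is p − p = 0 whatever q is.

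**3. Weight of one subject.** Cohort 1 has 4 placebo subjects and cohort 2 at least 4 (Table 2, Section 10.3). One unattributed vehicle reaction moves the placebo related-event rate in a group of 4 by 1/4 = 25 points. Pooled over 4 + 4 = 8, it moves it by 1/8 = 12.5 points.

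**4. Duration, worst case.** Take 6 months as 182 days. Suppose a reaction of true length t is an ADR in one arm and not in the other.

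Gap = min(t, 182) − min(t, 84)

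- t ≤ 84: 0 days
- t = 100: 100 − 84 = 16 days
- t = 140: 140 − 84 = 56 days
- t ≥ 182: 182 − 84 = 98 days

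The 140-day value comes from Section 1.2.4.1.2, which reports a single case of erythema and edema still seen up to Day 140 in the 180 mg cohort of the earlier Phase 2a trial, after abdominal injection.

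**5. Duration, on average.** Assume exponential durations with mean m, every active reaction an ADR and no vehicle reaction an ADR. Here 6 months is 365.25/2 = 182.6 days.

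Mean gap = m[exp(−84/m) − exp(−182.6/m)]

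- m = 14 days: 0.03 days; 0.2% of reactions open at Day 84
- m = 28 days: 1.4 days; 5.0% open
- m = 56 days: 10.3 days; 22.3% open

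The effect on duration is material only if reactions often outlast Day 84.

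**The case against.** A reader might infer that a vehicle reaction cannot be related at all, so that the placebo count is near zero by construction and the plan itself fixes follow-up at 6 months on active and 84 days on placebo. The documents do not support that.

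- Table 6 covers study procedures and reserves the unrelated category for clearly extraneous causes. A bruise after up to 48 vehicle injections does not fit that category.
- Section 6.2.3.1 includes placebo among investigational products, and other sections speak of study treatment.
- RZL-012 injection serves as shorthand for dosing in everyone. Appendix I uses it to define Day 0 for all subjects, and Section 9.5.1 uses it to set the Day 84 end point for all. The 6-month rule depends on ADR status, not on arm.
- The primary endpoint in Section 10.2.1 is not limited to related events. Local reactions are graded in both arms at the same visits through Day 84, and nothing says that later follow-up enters the arm comparison of duration.
- Single-blinding is a declared design choice, and safety analyses are descriptive (Section 10.5.6), so no error rate or power figure is affected.
- The Day 140 case was one event, on active drug, at another body site. The documents report no vehicle reaction that lasted beyond Day 84.

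All of this stands, and it limits the size of the problem. It does not remove the conflict inside Section 9.3, the omission of procedures from 9.1.3, or the missing window for duration. Because Table 6 points one way and the lead sentence the other, the result depends on which text an unmasked assessor follows.

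The visible Table 6 has no probable or possible category, although 9.1.3 relies on those terms. Rows may have been lost when the text was read from PDF, so this is not counted here.

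**Conclusion.** The point holds in a limited form. The causality target is inconsistent across 9.1.3, 9.3, Table 6 and 9.5.1, and an assessor who knows the arm applies it. The same judgement controls observation after Day 84. Related-event tables by arm can therefore be biased, by as much as p(1 − q) under the stated assumptions. The duration comparison can be biased only through reactions still open at Day 84.

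The 98-day and 56-day figures are worst-case illustrations: they need a long vehicle reaction that is also coded as not related despite Table 6. The direction is not certain. Under-attribution on vehicle would make RZL-012 look worse; reluctance to blame the drug would make it look better. With descriptive analyses the harm is a misleading table, not an inflated error rate. The change is still worth making, because duration is part of the primary endpoint and the cost is small.

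**What to change.** 1. Reconcile 9.1.3, 9.3, Table 6 and 9.5.1 so that relationship is judged to the study injection (RZL-012 or vehicle) or its procedure, with the same criteria in both arms.
2. Reconcile the wording on follow-up after Day 84 so that it does not depend on arm.
3. In Section 10.5, state that duration is compared between arms over the common window through Day 84, with a reaction still open then reported as ongoing at Day 84, and that later follow-up is listed descriptively.
4. Base the arm comparison of local reactions on all-causality events, and keep the by-relationship tables as supporting displays.

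Cost: wording changes and a note in the safety table specifications, and possibly a few extra follow-up contacts for placebo subjects with a reaction open at Day 84. Items 3 and 4 need no new data. The grading of reactions stays unmasked; these changes remove only the dependence on the causality call and on unequal observation time.

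### Sections 9.1.3 and 3.3.2 use probable and possible relatedness, levels that Section 9.3 does not name, so an uncertain event can be an ADR without being Related in Table 6

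*Combined protocol and SAP*

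**What the plan says.** Section 9.1.3 says that ADRs are adverse events "probably or possibly related to treatment as defined in Section 9.3". Section 3.3.2, under a heading about SAEs considered related to the drug, also speaks of possible and probable relatedness and defines neither.

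Section 9.3 is where the two levels should be found. Its prose has only the terms related and unrelated, which "refer to the association with the use of the investigational product, as defined below in Table 6". It continues: "Medical judgment should be used to determine the relationship, considering all relevant factors, including pattern of reaction, temporal relationship", with further factors after that. In Table 6, Related is for events that "are felt with high degree of certainty to be related to the study procedures/investigational product". The clarification beside it opens with "An AE may be considered related if or when all of the following apply" and lists four items: a plausible time sequence, no other reasonable explanation, "It disappears or decreases on cessation or reduction in dose", and "It follows a known pattern of response to the study procedures/investigational product". A sentence attached to the third item allows exceptions where an event persists after the product is stopped. Unrelated is for events plainly explained by something else. The clarification for that row is blank in the text available.

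Other sections then rely on these terms:
- Section 9.5.1 requires serious or severe ADRs to be reported within 24 hours, and ADRs to be followed to resolution or to 6 months after injection.
- Section 9.5.3 treats a SUSAR as an unexpected, related SAE and cites 9.1.2, 9.1.3 and 9.4.
- Section 7.3 says that ADR is defined in 9.3; Section 7.4 says 9.1.
- Section 10.5.4 reports related SAEs, and 10.5.6 tabulates AEs by relation to the drug.

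**The concern.** A classification that triggers reporting and follow-up should give the same answer whichever section a site consults. Here a site that starts from 9.1.3 would treat a possible reaction as an ADR. A site that starts from Table 6 would look for high certainty and might not. Both would be following the protocol.

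The call is made by investigators who know the treatment given (Sections 6.2.2 and 9.3), which makes a clear threshold more important. Safety is the primary objective (2.2.1), and this is the first trial to go up to 240 mg (1.2.4). With 12 and 16 subjects in the two cohorts (10.3), moving one event across the line visibly changes a table.

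The wording of Table 6 also points away from reactions of a new kind, yet a SUSAR is by definition a reaction that is both related and unexpected.

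**Working it through.** No arithmetic applies; the plan gives no figure to reproduce. The check compares the definitions and then traces which rules use them.

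**Step 1: are the levels defined?** Section 9.1.3 relies on two levels, probably and possibly, and sends the reader to 9.3. The prose of 9.3 names neither, and nor do the two visible rows of Table 6. Section 3.3.2 uses both levels but gives no definition.

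**Step 2: how do events classify?** Give possibly its ordinary meaning, which is an assumption because 9.1.3 supplies no test of its own.

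| Event | ADR under 9.1.3 | Related in Table 6 | Unrelated in Table 6 |
|---|---|---|---|
| Highly certain, known kind | Yes | Yes | No |
| Plausible, not certain | Yes | No, certainty not reached | Not on the visible definition |
| Plausible, of a new kind | Yes | Discouraged by the known-pattern item | Not on the visible definition |
| Plainly due to something else | No | No | Yes |

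The two definitions agree in the first and last rows and can part in the middle two.

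**Step 3: does the known-pattern item fit the reporting rules?** Under 9.4 a reaction is unexpected if its nature or severity departs from the Investigator's Brochure. Section 9.5.3 needs such an event to be related as well. A reaction of an unexpected nature is the one least likely to follow a known pattern, so the item works against the category that 9.5.3 is meant to catch.

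**Step 4: does the cessation item fit the design?** Section 3.3.1 gives a single dose. After Day 0 there is no dosing to stop or reduce, so the item can only be read as resolution over time.

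**Step 5: what depends on the classification?**
- Affected: the 24-hour report of severe non-serious ADRs and the ADR follow-up rule (9.5.1); SUSAR labelling (9.5.3); the related-event tables (10.5.4 and 10.5.6).
- Not affected: recording of all AEs (9.5.1); SAE reporting to the sponsor, which is required whatever the relationship (9.5.2); the local skin endpoints (10.2.1).
- Sections 7.3 and 7.4 lead back to the same definitions. They inherit the gap and do not add a competing definition.

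**The case against.** The strongest reply is that 9.1.3 sets no threshold. It defers to 9.3, so on a strict reading there are two undefined words and not two rival tests. That is fair, and it is why the split in Step 2 is stated as resting on the ordinary meaning of possibly. The strict reading does not help the plan, however: it leaves the definition of ADR without content.

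A second reply is that part of Table 6 is lost in the text available. A reader might infer that the plan has no rule for uncertain events. The documents do not support that, because such a rule could lie in the missing clarification for Unrelated. What survives is the mismatch itself: the two-term sentence is intact prose, and the high-certainty description of Related is legible.

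A third reply is that the four items are guidance. A reader might infer that Table 6 bars a Related call for any new or persistent reaction. It does not. The lead-in says that an event may be considered related if or when the items apply, not only if they do, and 9.3 asks for medical judgment. The exceptions sentence softens the cessation item, though not the known-pattern item. The list therefore discourages such a call without forbidding it.

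A reader might also take 3.3.2 to presume that every SAE is related. Its heading limits it to SAEs considered related, so the more natural reading is that possible or probable relatedness is enough. That agrees with 9.1.3 and leaves the Related row of Table 6 as the outlier. It narrows the effect on SUSAR labelling, as does the sponsor side supplying SAE expectedness (6.1.14) and filing regulatory expedited reports (9.5.3).

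**Conclusion.** The inconsistency is real and should be fixed. Sections 9.1.3 and 3.3.2 rely on two causality levels that the prose of 9.3 does not name, and Table 6 describes Related in terms of high certainty. On the ordinary meaning of possibly, an uncertain AE is an ADR but not Related.

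The consequence is bounded. It falls mainly on severe non-serious reactions, ADR follow-up, SUSAR labels and the descriptive tables of related events. A reader might infer that reactions will be systematically under-reported. The documents do not show this. Table 6 is tighter than 9.1.3 on certainty but wider in scope, since it also covers study procedures, and medical judgment applies throughout. Neither the number nor the net direction of misclassified events can be derived.

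The conclusion assumes that the missing Table 6 text does not define probable and possible. If it does, the table conflicts with the two-term prose of 9.3, and the link between those levels and related in 9.5.3, 10.5.4 and 10.5.6 would still need to be stated.

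**What to change.** First check the Table 6 source page. Then:

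1. Reconcile 3.3.2, 9.1.3 and 9.3 with Table 6 to one causality scale, used in both the protocol and the CRF. Two levels or a graded scale would both serve.
2. Use the same threshold on that scale for ADR, for SUSAR and for related in 10.5.4 and 10.5.6.
3. Make clear that a known pattern, and improvement on stopping or reducing the dose, are supporting considerations and are not required for a Related call in this single-dose trial.
4. Point 7.3 and 7.4 to that one definition.

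The cost is protocol wording and a CRF code list. The downside is that more events may be counted as related, depending on the threshold chosen. No position is taken on the follow-up, discontinuation or termination rules themselves.
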